injection of Exparel can provide adequate pain relief over 3 days it can make obsolete the need to place a continuous nerve block catheter. There are significant benefits to this. It requires more skill and time to place a catheter versus a single injection of a local anesthetic for a TAP block. Other benefits are related to the avoidance of catheter maintenance including dressings, leakage at catheter insertion site, and the need for additional infusion pumps. Furthermore, any catheter has the possibility of infection or bleeding.

It is the purpose of this study to evaluate the efficacy of methods that allow for continuous release of local anesthetic in the TAP space, either via catheter or via injecting Exparel® a slow release liposomal space versus the standard single injection Bupivacaine in the TAP space. The study shall consist of three (3) arms of which patients will be randomly assigned: Continuous TAP block (CTAP) via Catheter, Single Injection TAP block with the slow release liposomal Exparel, and Single Injection TAP block with Bupivacaine. Several parameters will be measured with the primary goal being to determine the effectiveness and duration of post-operative pain relief.^{8,9}

Primary Hypothesis

Methods that allow for continuous release of local anesthetic in the TAP space will decrease total narcotic requirements vs. the standard single shot Bupivacaine control. A continuous release of local anesthetic in the TAP space via catheters over 2 days will result in lower total narcotic requirements when compared to the single shot Bupivacaine injection technique when measured over 48 hrs. The Liposomal agent Exparel® which releases the Bupivacaine local anesthetic over three days should also allow for a single injection technique that can provide similar post-operative pain response to that of the catheter method without the need to place a catheter in the TAP space. Post-operative narcotic requirements are inversely related to post-operative pain control and patient satisfaction and total narcotic requirements will be significantly higher in the single shot group vs. the continuous release groups over 48 hrs.

Purpose of the Study Protocol

The purpose of this study protocol is to ensure consistent implementation of this study across all study sites.

B Background

Prior Literature and Studies

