Subjects will be consented using a current informed consent form that has been approved by the respective study site's Institutional Review Board. Subjects will be allowed adequate time to read the informed consent, discuss the consent with study staff and others (e.g., family members, friends, or any of their health care providers), and have their questions answered prior to signing the informed consent. In some cases, a site may not accrue study subjects but serve as a data analysis site so informed consent may be waived for that site.

Site-specific recruitment plans and consent process are outlined in Attachment L1.

E2.e Randomization Method and Blinding

Subjects that would normally be selected to receive a TAP block will be randomly assigned into one of the three arms. A random number generator will be used to generate an equal proportion of responses of the three arms. These responses will be sealed in envelope. The anesthesia provider will be allowed to open the envelope and become aware of the selected arm after the initiation of anesthesia (this would include the administration of a pre-medication or initiation of general anesthesia). Complete blinding is impossible to staff given the visual presence of a catheter in some groups versus the lack of catheters in other groups. In addition, the agent Exparel® has a milky color that is obvious to the anesthesia provider injecting it. However, the nursing staff on the floor will not be made aware of the use of Exparel® versus Bupivacaine in the single injection arms.

E2.f Risks and Benefits

i Risks

Potential physical risks include:

TAP block is a relatively low risk regional anesthesia technique with a long track record. However, any injection or insertion of a catheter into the body carries a slight risk of bleeding, bruising at injection or insertion site, and infection at injection or insertion site. Risks particular to an injection of a local anesthetic into the abdominal area would be bowel perforation, local anesthetic toxicity, and drug allergy. These risks are unlikely and similar to an abdominal paracentesis. Furthermore, the author is unaware of any episodes of bowel perforation from the administration of a TAP block.

The following are side effects have been seen with the local anesthetics Bupivacaine and Ropivacaine:

- Low blood pressure
- Nausea and/or vomiting
- Slow heartbeat
- Fever
- Pain
- Post-operative complications
- Low blood hemoglobin (anemia)

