All post-surgical patients are given a Dilaudid (or the equivalent dose of Morphine if not tolerated) IV PCA with every 10 minutes bolus function following surgery to be initiated immediately upon admission and transfer from the PACU to the floor. A clinician bolus of Dilaudid 0.5 mg every 30 minutes will be made available for additional pain control if needed.

Acetaminophen (Tylenol) will also be made available for treatment of post-operative pain on the floor.

Treatment Regimen

Patients assigned to the study group will randomly be assigned to one of the three arms described above. Patients in the catheter arm will receive a commercially available ON-Q® pain management system filled with 0.2% Ropivacaine. The ON-Q® system consists of an ON-Q® elastomeric infusion pump that will be connected to an end-orifice catheter. Patients in the catheter arm will receive a 20 ml bolus of Bupivacaine via Tuohy needle in the TAP space followed immediately by tunneling of a catheter into the TAP space under ultrasound guidance prior to extubation and complete emergence from general anesthesia. Said catheter will be left to infuse continuous local anesthetic site up to post-operative day 3. Patients in the two (2) single injection arms will similarly receive a bilateral injection of study local anesthetic (Exparel or Bupivacaine) 25-30ml per side in the TAP space prior to the conclusion of surgery under ultrasound guidance. Intra-operatively patients in all three study arms will receive IV fentanyl and IV Acetaminophen 1000mg unless drug allergy or intolerance to either medication.

Initial rescue IV pain medication will be made available similarly in all three study arms according to the institution's protocol for PACU breakthrough pain and will consist primarily of IV Dilaudid (or Morphine equivalent if patient does not tolerate Dilaudid). All post-surgical patients are given a Dilaudid (or Morphine if not tolerated) IV PCA with q10min bolus function following surgery to be initiated immediately upon admission and transfer from the PACU to the floor. A clinician bolus of Dilaudid 0.5 mg every 30 minutes (or Morphine equivalent) will be made available for additional pain control if needed. Tylenol will also be made available for treatment of post-operative pain on the floor.

E3.b Method for Assigning Subjects to Treatment Groups

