Randomization will occur following the consent process and prior to surgery. The on-site personnel will manage the randomization. A random number generator will be used to assign patients to one of three arms and the anesthesia provider will be unaware of which arm the patient is assigned to until after initiation of anesthesia (see section E2.e).

E3.c Preparation and Administration of Study Drug

Patients in the single shot arms (Bupivacaine 0.25% and Exparel) will receive bilateral bolus injections of the local anesthetic t prior to extubation (waking up from General Anesthesia). Patients in the continuous catheter arm will also receive a bolus injection of local anesthetic prior to the placement of the catheter. Those patients will also receive a pump.

- 1) Bupivacaine 0.25% Arm: A total of 60 ml Bupivacaine 0.25% from two 30 ml vials will be pre-drawn up via 60 ml Syringe. The syringe will be connected and a 10ml flush syringe containing 10ml 0.9 NS will be connected to the end of an IV extension set via a 3-way stopcock and luer lock connections. The Bupivacaine 0.25% syringe will also be connected to the stopcock. The distal end of the IV connection will be maintained sterile and will be connected to the injection needle. Then the procedure is as follows: Step 1) The entire setup will be flushed with 0.9NS via flush syringe. 2) The TAP space will be located under ultrasound guidance and verified by using the 0.9% NS flush syringe. Once in the TAP space, 30 ml Bupivacaine 0.25% will be injected into the TAP space (This dose will be decreased to 25ml for patients under 70 kg). Steps 2 and 3 will be repeated on the opposite side TAP block.
- 2) Exparel Arm: The entire contents of one 20 ml Exparel vial (266 mg) will be drawn up 20 ml syringe. 40ml Bupivacaine 0.25% will be pre-drawn into 2x 20 ml syringes and connected to a stopcock. The syringe containing the Exparel solution will also be connected to the stopcock. The distal end of the IV connection will be maintained sterile and will be connected to the injection needle. Procedure Step: 1) The entire setup

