Patient characteristics and outcomes data will be summarized by cross-tabulation (categorical variables), quartiles (median, ordinal variables), and mean and standard deviation (continuous variables). Comparisons between groups will use Chi-square test or Fisher's exact test as appropriate for categorical variables and t-test or Wilcoxon rank-sum test as appropriate for continuous variables.

Analyses of primary outcome will examine differences in mean opioid consumption between the single shot TAP group and the Exparel TAP group. Analyses of secondary outcomes will examine differences in mean opioid consumption between the single shot TAP group and continuous TAP group. Treatment groups will be compared using a

student's t-test if data are normal distributed or Wilcoxon rank-sum test if not normal distributed.

The differences in mean opioid consumption across three groups (single shot TAP, continuous TAP, and Exparel TAP) will be examined with a test of means between groups using one-way analysis of variance (ANOVA). A comparison between continuous TAP and Exparel TAP will be performed. A t-test will be used if the observations in each trial arm are normally distributed; if non-normally distributed, then rank-based methods such as Wilcoxon rank-sum test will be employed.

All tests will be two-sided.

The overall incidence of serious adverse events and adverse events and number and proportion of patients reporting such events will be summarized by treatment group. Adverse events will be tabulated and summarized by the number and percentage of subjects who experienced the event.

Missing Outcome Data

Analysis will be conducted as described in prior section. Missing data will not be included in the analysis; however, may lead to an increase in patients recruited into one or more study arms.

Unblinding Procedures

This study is not blinded because it will be obvious to all care givers whether or not the patient received a continuous block with catheters or not.

H Data Handling and Record Keeping

Confidentiality and Security

Data will be collected on the data collection forms located in Attachment L9 and entered into the Oncore ERM study management system.

Data collection forms will be stored at each respective study site within a locked cabinet in a locked research office.

The Oncore ERM study management system is a secure web-based management system that is password-protected. Access to data is role-specific.

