All study sites will observe Health Insurance Portability and Accountability Act (HIPAA) Privacy and Security Rule standards.

Training

All research team members must complete approved Human Subjects and HIPAA training.

All research team members must complete Oncore ERM training.

Case Report Forms and Source Documents

Study sites will utilize the data collection forms in Attachment L9 to collect data and will enter data into the Oncore ERM study management system.

Records Retention

Paper study records will be maintained at the respective study sites for seven years from the end date of the study. At the end of this time period, study records will be shredded.

Data in the Oncore ERM study management system will be stored for seven years from the end date of the study. At the end of this time period, records will be deleted.

Performance Monitoring

The IRB and the Principal Investigator will monitor study performance using the Oncore ERM study management system.

I Study Monitoring, Auditing, and Inspecting

Study Monitoring Plan

The IRB and the Principal Investigator will monitor ongoing study performance using the Oncore ERM study management system.

Auditing and Inspecting

The IRB will audit and inspect study materials at the study sites as indicated.

J Study Administration

Organization and Participating Centers

The Principal Investigator at the lead institution will collaborate with study site Principal Investigators to oversee this study.

Funding Source and Conflicts of Interest

There are no conflicts of interest among any of the study investigators.

Study investigators must complete institution-specific conflict of interest forms as required.

Subject Stipends or Payments

Subjects will not be paid for their participation in the study.

Study Timetable

The study will last for approximately four months. This is the estimated time based on current operating room patient criteria to enroll ninety patients into the study.

κ Publication Plan

Upon completion of study and statistical methods, it would be expected to publish the study in an established and well-read peer journal of either Anesthesiology or Surgery. Given that an analysis demonstrating a statistically significant difference or no difference between any of the study arms would be useful to how anesthesiologist and/or the surgical team approach the TAP block, it is highly likely the study would be accepted for publication.

L Attachments – TAP Block Pain Management Data Form

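### The plan is written for several sites but neither stratifies allocation by site nor includes site in any analysis; if more than one site accrues, this may forgo some precision on the opioid endpoint

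*Combined protocol and SAP*

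**What the plan says.** **Sites.** The Purpose of the Study Protocol section says that the document exists to "ensure consistent implementation of this study across all study sites". Under Organization and Participating Centers, the lead investigator "will collaborate with study site Principal Investigators to oversee this study". Section E2.d refers to site-specific recruitment plans and site IRBs, but also allows that in some cases "a site may not accrue study subjects but serve as a data analysis site". The number of accruing sites is not given.

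**Allocation.** Section E2.e states: "A random number generator will be used to generate an equal proportion of responses of the three arms", with the results placed in sealed envelopes. Section E3.b adds: "The on-site personnel will manage the randomization". Neither section mentions blocks or strata, or says whether there is one central list or one list per site.

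**Rescue opioid.** Under Treatment Regimen, PACU rescue is given "according to the institution's protocol for PACU breakthrough pain". On the floor, Treatment Regimen and E3.c set one framework for all arms: hydromorphone PCA with a 10-minute interval and a 0.5 mg clinician bolus every 30 minutes. The PCA bolus size is not stated.

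**Analysis.** In section G, "Analyses of primary outcome will examine differences in mean opioid consumption between the single shot TAP group and the Exparel TAP group", by t-test or Wilcoxon rank-sum test. The three-arm comparison is a one-way ANOVA. No planned test has a site term. The data form in section L records surgeon and anesthesiologist but shows no field for site.

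**The concern.** The endpoint is milligrams of opioid, which depends on local prescribing as well as on the block. If several hospitals enrol, differences in PACU practice, PCA settings or mix of operations could move consumption for reasons unrelated to the arm. An analysis without site leaves that variation in the error term.

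The consequence depends on how the lists are made. If they are balanced within site and site is then ignored, the standard error is too wide and the test is conservative. If they are not balanced within site, the arms can differ by chance in site mix. In either case a model with site could give a tighter estimate from the same patients. Stratified allocation has to be in place before enrolment starts, so the question is best settled in the protocol.

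**Working it through.** **Inputs from section G, Sample Size:** means 4.1 and 2.4 mg, so δ = 1.7 mg; SD 3 mg in both arms; two-sided α 0.05; 80% power; 49 per arm; 10% dropout; 53 per arm recruited.

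**1. The plan's own figure.** n = 2 × SD² × (1.960 + 0.842)² / δ² = 2 × 9 × 7.849 / 2.89 = 48.9, so 49 per arm. This reproduces the plan (normal-approximation power 80.1% at 49). The exact t-test gives 79.3% at 49 and reaches 80% at 50.

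**2. Patients left after dropout.** 53 × 0.9 = 47.7, so about 48 per arm. The standard error is 3 × √(2/48) = 0.612 mg and δ/SE = 2.78. Exact t-test power is 78.5%.

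**3. Site in the model.** Let ρ be the share of the total variance (9 mg²) that lies between sites. The documents give no value, so ρ is assumed over a range. A site term reduces the residual SD to 3 × √(1 − ρ). Power is from the noncentral t with 48 per arm.

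| Assumed ρ | Residual SD (mg) | SE (mg) | Power |
|---|---|---|---|
| 0 | 3.00 | 0.612 | 78.5% |
| 0.01 | 2.98 | 0.609 | 78.9% |
| 0.02 | 2.97 | 0.606 | 79.3% |
| 0.05 | 2.92 | 0.597 | 80.5% |
| 0.10 | 2.85 | 0.581 | 82.5% |
| 0.20 | 2.68 | 0.548 | 86.7% |

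The degrees of freedom lost to two or four sites change these figures by less than 0.1 point. With one accruing site the first row applies and nothing is gained.

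**4. Lists balanced within site, site ignored.** The true SE is √(1 − ρ) times the one the test uses, so true type I error is about 2 × [1 − Φ(1.96/√(1 − ρ))]. This is 4.4% at ρ = 0.05, 3.9% at 0.10 and 2.8% at 0.20. Simulations with two or four equal sites (49 per arm, 6,000 runs per setting) gave 4.2-5.0%, 3.5-4.0% and 2.6-2.8%.

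**5. Lists not balanced within site, site ignored.** In the same simulations type I error stayed near 5% (4.7-5.5%) and power near 79-80%. As an illustration of chance imbalance, take two equal sites and 53 per arm. Two arms then differ by more than 15 percentage points in site mix in about 14% of trials. At ρ = 0.10 the two sites are 2 × 3 × √0.10 = 1.9 mg apart, so a 15-point imbalance moves the contrast by 0.15 × 1.9 = 0.28 mg, or 17% of 1.7 mg.

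**6. Cost when sites do not differ (ρ = 0, four sites, 49 per arm, simulated).** Under unstratified allocation, adding site took power from 79.6% to 78.0%. Under lists balanced within site it was 79.2% with or without the site term.

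**The case against.** **There may be only one accruing site.** The multi-site wording is general, E2.d allows sites that do not enrol, and the only hospital named is the lead one. This stands: the point is conditional on more than one accruing site.

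**Rescue is largely common.** A reader might infer that all rescue analgesia follows each hospital's own rules. The text does not say so. The reference to an institutional protocol is singular and covers the PACU only; the floor framework is the same for all arms. An unstated PCA bolus size leaves room for variation between sites but does not show any.

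**The variance share is unsupported.** Also true. With two equal sites, ρ = 0.10 means hospitals 1.9 mg apart, more than the planned effect, and ρ = 0.20 means 2.7 mg. Shares of 1-2% are worth less than one point of power.

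**Power is not really short.** SD 3 is called conservative. With the plan's own SDs of 3 and 1.3 mg, SE = √((9 + 1.69)/48) = 0.472 mg and power is about 95% by the normal approximation. This weakens any urgency, although added precision would still narrow the interval.

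**Allocation may already be by site.** On-site management is compatible with separate site lists. The documents do not settle this, so a reader should not infer one unstratified list. If the lists are by site and balanced, the unadjusted test is conservative.

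**A site term can cost power.** It can, by about 1.6 points in the simulated four-site case with no site variance, but only under unstratified allocation. With blocked lists per site the loss essentially disappears.

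**Conclusion.** The documents establish three things: the plan is worded for several sites, randomisation is managed on site, and neither the stated allocation nor any planned test uses site. If more than one site accrues and sites differ in opioid use, precision may be forgone: under 1 point of power for assumed shares of 1-2%, about 2 points at 5%, 4 at 10% and 8 at 20%, all at 48 per arm. With one accruing site the gain is nil.

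Two stronger readings are tempting. One is that ignoring site biases the comparison or inflates type I error. It does not: randomisation protects the contrast, chance imbalance in site mix is already reflected in the standard error, and the test is at its nominal level or conservative. The other is that the sample size is wrong. It is not: SD 3 mg is a total SD that already includes any site variance, and 49 per arm reproduces. This is a cheap improvement to a valid plan.

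**What to change.** **Sections E2.e and E3.b:** state the number of accruing sites and how the lists are generated. If there is more than one, use a separate permuted-block list with varying block sizes for each site, prepared in advance by someone who does not enrol patients. Add a site field to the data form.

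**Section G:** estimate the primary mean difference from a linear model with arm and site, and name the site-stratified van Elteren test as the rank version. If only one site accrues, say so; the site term then drops out.

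**Cost:** one set of envelopes per site, one degree of freedom per extra site and one added model term. Under blocked lists there is essentially no power loss if sites turn out not to differ. The sample size need not change.
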